7.3. Treatment of AE

A patient with an AE must receive appropriate therapy. The patient will remain under medical supervision until the investigator determines that the AE has been resolved.

7.4. Assessment of seriousness

AE is considered serious if it fulfils the definition in Chapter 7.1.

Some situations can be **considered as SAE even if they do not fulfil the criteria** of the definition. These are important medical events that may not be immediately life-threatening, or result in death, or hospitalization but may endanger the subject, or may require intervention to prevent one of the other outcomes listed in the definition above. These should also be considered SAE – e.g., allergic bronchospasm, convulsions, or other states requiring treatment. If AE fulfils the criteria of SAE, a separate **Serious Adverse Event Form** have to be completed and sent to the sponsor. For the procedure see Chapter 7.7.

7.5. Assessment of intensity (severity)

The intensity (severity) of an AE should be evaluated according to these 5 categories:

Grade 1	AE is asymptomatic or mildly symptomatic, requires only observation, no medical intervention
Grade 2	AE with medium intensity, requires local, non-invasive, or small-scale treatment
Grade 3	AE is medically significant, requires hospitalization or extension of ongoing hospitalization, but it is not directly life-threatening

Grade 4	AE is life-threatening and requires urgent significant medical intervention
Grade 5	AE leads to death

7.6. Assessments of causality

To assess the relation between administration of the study medication and the AE, the following definitions apply:

- **Related** – The event is known to occur with the study medication, there is a reasonable possibility that the study medication caused the AE, or there is a temporal relationship between the study medication and AE. Reasonable possibility means that there is evidence to suggest a causal relationship between the study medication and the AE.
- **Not related** – There is not a reasonable possibility that the administration of the study medication caused the AE, there is no temporal relationship between the study medication and AE onset, or an alternate aetiology has been established.

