7.1. Definitions (according to the Regulation EU No. 536/2014)

For clinical trials, effective legislation has introduced the following definitions.

Table 2: Definitions of safety events

Adverse event	AE	Any untoward medical occurrence in a patient or clinical trial subject administered a medicinal product and which does not necessarily have a causal relationship with this treatment.
Adverse drug reaction	ADR	All untoward and unintended responses to an investigational medicinal product related to any dose administered
Serious adverse event	SAE	A serious adverse event/reaction is any untoward medical occurrence or effect that at any dose: 
• Results in death;• Is life-threatening;• Requires hospitalization or extension of existing hospitalization;• Results in persistent or significant disability or incapacity;• Is a congenital anomaly or birth defect.
Serious adverse reaction	SADR	
Unexpected adverse reaction	UADR	Adverse reaction, the nature, severity, or outcome of which is not consistent with the product information (SmPC)
Suspected unexpected serious adverse reaction	SUSAR	Any suspected adverse reaction related to the study treatment that is both serious and unexpected.

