8.3. Analysis of secondary objective(s) and endpoint(s)

All secondary endpoints will be analysed using FAS. Descriptive statistics and statistical tests described above will be used based on the type of variables and fulfilment of criteria for the usage of particular tests.

The incidence of any adverse events and reactions will be analysed descriptively and compared between study arms in the same manner as the primary endpoint

Duration of surgery will be analysed descriptively and compared between study arms.

ICU and hospital length of stay (LOS) will be calculated as a number of days between admission and discharge, analysed descriptively and compared between study groups.

28-days mortality will be evaluated as a number and percentage of patients who are not alive 28 days after randomization and compared between study arms.

Hemodynamic characteristics, blood parameters (hemoglobin, plasma lactate level) and their changes over time will be analysed descriptively and compared between study arms.

Fluid balance and fluid therapy will be analysed descriptively and compared between study arms.

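### The causality categories 'Related' and 'Not related' in section 7.6 overlap and no precedence is stated, so some events meet both definitions

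*Protocol*

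**What the plan says.** Protocol section 7.6 gives investigators two causality categories.

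- **Related** has three routes joined by 'or'. The first is "The event is known to occur with the study medication". The second is a reasonable possibility that the medication caused the event, which the section explains as evidence suggesting a causal relationship. The third is "or there is a temporal relationship between the study medication and AE".
- **Not related** also has three routes joined by 'or'. The first is "There is not a reasonable possibility that the administration of the study medication caused the AE". The other two are "there is no temporal relationship between the study medication and AE onset, or an alternate aetiology has been established".

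No sentence says which category applies when an event qualifies for both, and no time window is given for a temporal relationship.

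Other parts of the protocol use the result. Section 7.2 requires a causality assessment for every adverse event. Section 7.1 defines an adverse drug reaction as "All untoward and unintended responses to an investigational medicinal product related to any dose administered" and a SUSAR as "Any suspected adverse reaction related to the study treatment that is both serious and unexpected". Section 2.3 lists a descriptive analysis of adverse events and reactions among the secondary endpoints, and section 8.3 adds: "The incidence of any adverse events and reactions will be analysed descriptively and compared between study arms in the same manner as the primary endpoint".

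**The concern.** A two-way classification works only if each event falls on one side. Here each side can be reached by a single criterion, and the criteria of one list do not exclude those of the other.

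The conflict is easy to meet in this trial. Section 6.3 provides for study fluids around surgery in both arms: a basal crystalloid infusion with boluses under GDHT, and boluses for hypotension under standard care. Take postoperative haemorrhage, which Appendix A limits to 72 hours from the start of surgery. If it follows a study infusion, it can be called 'Related' by timing. If a surgical source is established, the same event is 'Not related' by aetiology. Two investigators who follow the text faithfully can record opposite answers.

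At stake are the classification of such events as adverse reactions, the causality element of SUSAR status, and any between-arm count of reactions. Investigators apply these definitions while the trial runs, so an analysis plan cannot repair the classifications afterwards.

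**Working it through.** The protocol states no figure on this point, so there is none to reproduce. The check is of the logic of the two definitions.

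**Inputs (section 7.6).** Four yes/no facts about an event:

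- K: known to occur with the medication
- R: reasonable possibility that the medication caused it
- T: temporal relationship
- A: alternate aetiology established

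**Definitions as written.**

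- Related = K or R or T
- Not related = (not R) or (not T) or A

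**Enumeration.** Four yes/no facts give 2 × 2 × 2 × 2 = 16 combinations.

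| Result | Combinations | Which ones |
|---|---|---|
| Related only | 2 | R and T present, A absent, K either way |
| Not related only | 2 | K, R and T all absent, A either way |
| Both | 12 | all others (16 − 2 − 2) |
| Neither | 0 | none |

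**The case of timing plus another cause.** With T and A both present, 4 combinations remain (K and R either way). All 4 meet both definitions. With T present and A either way there are 8 combinations: 6 meet both, 2 are Related only, and none is Not related only.

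**Does a stricter reading remove the overlap?** Some of the 16 combinations may be thought clinically impossible, so they were removed in steps.

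1. Assume that an established alternate aetiology rules out a reasonable possibility. This drops the 4 combinations with A and R, leaving 12, of which 8 meet both.
2. Assume also that a reasonable possibility requires a temporal relationship. This drops 2 more, leaving 10, of which 6 meet both.

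The overlap survives both assumptions.

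**The same check after the fix.** If Related = R and Not related = not R, the 16 combinations split into 8 and 8, with none in both and none in neither.

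**Is there a rule elsewhere that decides?** Section 9.5 sends ambiguous SAEs to the investigator in consultation with the pharmacovigilance manager and the medical monitor. It names who discusses the case but not the criterion to apply, and it does not cover non-serious events, which the secondary endpoint also counts.

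**The case against.** The strongest reply is that 7.6 already contains a usable standard. Reasonable possibility is defined there, and its absence is the first route to 'Not related'. A sensible investigator would decide on that basis and treat timing as supporting evidence. Serious cases that remain unclear go to consultation under 9.5. The affected output is one secondary safety item, and section 8 calls all testing exploratory.

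Much of this stands, and it limits the consequences. It does not remove the contradiction, because the text makes timing sufficient by itself for one category and an alternate cause sufficient by itself for the other.

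A reader might be tempted to infer more. Three stronger readings are not supported:

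- **That about 31 patients are affected.** Averaging the planning rates in 8.1 gives (33% + 11%)/2 = 22%, and 0.22 × 140 = 30.8. That is an expected number of patients with any AESI and says nothing about how causality would be judged. AESI are collected to day 28 and include late infections and thrombosis, whose temporal link to an intraoperative infusion is not self-evident.
- **That every serious event following the infusion and absent from the product information becomes a SUSAR.** Section 7.1 also requires a suspected adverse reaction, that is, an untoward and unintended response to the product. The procedure under the SUSAR heading in 7.7 is not in the text available for this review, so a further causality step there cannot be excluded.
- **That safety reporting would be flooded.** Under 7.7 investigators report every SAE to the sponsor within 24 hours whatever its cause, so that volume does not change.

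**Conclusion.** Wrong as written, with limited reach. The two categories in 7.6 are not mutually exclusive and no precedence is stated. For an event with both a temporal relationship to the study fluid and an established alternate aetiology, the definitions do not determine whether it is an adverse reaction. The causality part of SUSAR status and the exploratory comparison of reactions between arms inherit that gap.

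The size can be stated only in terms of wording: 12 of 16 logical combinations meet both definitions, and 6 of 10 under the strictest assumptions tried. These are not event frequencies. The protocol gives no data from which to derive a number of affected patients.

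Unaffected are the primary endpoint, which counts patients with any AESI regardless of cause (8.2), the total count of adverse events, and 24-hour SAE reporting to the sponsor (7.7). The conclusion assumes that 'or' in 7.6 is read literally and that no precedence rule stands in the SUSAR text that could not be seen.

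**What to change.** Make reasonable possibility, in the sense 7.6 already gives it, the single deciding criterion:

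- **Related:** a reasonable possibility exists that the study medication caused the event.
- **Not related:** no such reasonable possibility exists.

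Then add that timing, known effects of the product and any alternate aetiology are to be weighed in reaching that judgement, and that none of them decides the category alone. Align the eCRF help text.

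The cost is a rewording of two definitions and one help text. No treatment rule, endpoint definition or sample size changes. If events have already been classified under the present wording, those with both a temporal relationship and a recorded alternate cause should be re-assessed under the new wording, so that one rule applies throughout.

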7.7. Reporting of SAE and SUSAR

The investigator is obliged to report any SAE within 24 hours after he/she learns about it to the sponsor using Serious Adverse Event Form (SAE Form). The blank forms are stored in the Investigator's Site File. Reporting should be done by e-mail: [contact] AND [contact].

Sponsor will check the SAE Form completeness and formal plausibility. If required, queries will be made.

If all required information is not available at the time of the initial SAE report, follow-up reports should be sent by the investigator. Follow-up report should use a new blank SAE Form and the investigator should clearly state that this is a follow-up and give the date of the initial report. The investigator must update the SAE form and submit any supporting documentation (e.g., lab results, subject discharge summary, autopsy report) within 24 hours of receipt of this new information. The follow-up SAE report should describe whether the event has resolved or continues, if and how it was treated and whether the patient continued or withdrew from trial participation.

All SAEs should be followed until their resolution, i.e., they subside, stabilize, become chronic, or the subject dies followed. In case of early termination because of SAE occurrence, the subject should be followed until SAE resolution. All necessary extra visits will be recorded in the eCRF as "Unscheduled visits".

In the case of death, a copy of the autopsy record should be added, if available. If the death of the subject complies with the definition of SUSAR (see Chapter 7.1), it will be reported as SUSAR (see below).

Sponsor has full responsibility for the safety of the clinical trial. Further reporting of AEs to the competent authorities according to the legal requirements is the responsibility of the sponsor.

Reporting of SUSAR

7.8. Pregnancy

The Investigator should report the pregnancy to the Sponsor within 24 hours of learning of its occurrence using Pregnancy Form. This announcement will be done by e-mail: [contact] AND [contact].

Pregnancy and breastfeeding are exclusion criteria, and thus, pregnant and breastfeeding women cannot be included in the study. Pregnancy testing (hCG, urine sample) is obligatory at enrolment in women of childbearing potential³. Newly-emerged pregnancy in the hospitalization and follow-up phase of the trial is highly unlikely. However, if a subject becomes pregnant during the trial course, she must inform the investigator.

Pregnancy should be followed by the investigator until completion. If it ends for any reason before the anticipated date, the investigator should notify the sponsor. At the completion of the pregnancy, the investigator will document the outcome of the pregnancy. If the outcome of the pregnancy meets the criteria for classification as SAE (e.g., spontaneous abortion, stillbirth,

³ Childbearing potential is limited by the period from menarche to the onset of postmenopause (i.e. the period in which menstruation last occurred physiologically at least 12 months ago). The onset of postmenopause will not be verified by FSH testing, in case of doubt, the physician will consider the woman as a woman with childbearing potential.

neonatal death, postpartum complication, or congenital anomaly), the investigator should follow the procedures for reporting an SAE (see Chapter 7.7).

8. STATISTICS

A separate Statistical Analysis Plan (SAP) will be prepared to provide details on the approach to analyses. The SAP will be finalized before the database lock. All eventual deviations from the SAP will be described and justified in the relevant part of the Clinical Trial Report.

As a general approach for the descriptive analysis, the following statistics will be provided for continuous variables: number of subjects with available data (n), mean, standard deviation, median, 25% and 75% quartile, minimum and maximum. Categorical and binary variables will be presented as absolute and relative frequencies together with 95% CI, if appropriate.

For comparison between study arms two-sample Welch's t-test or its nonparametric alternative (Mann-Whitney test) will be used for continuous variables, Pearson's Chi-square test or Fisher exact test, if the assumptions for Chi-square test are not met, for categorical parameters.

Welch's t-test will be used if the normality is not rejected; otherwise Mann-Whitney test will be used for comparison of continuous variables. The normality will be checked visually (using histograms and Q-Q plots) and explored using Shapiro-Wilk test and eventually evaluated as a combination of visual assessment and statistical testing. If the normality of the data is not rejected, the difference between study groups will be expressed using difference between the means and 95% CI. Otherwise, the difference between the medians will be presented together with 95% CI calculated using bootstrap method.

As there is no formal statistical hypothesis to be tested, all statistical tests will be two-sided and performed on exploratory basis only. P-values < 0.05 will constitute statistically significant differences.

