2.3. Secondary objective(s) and endpoint(s)

The **secondary objective** is to investigate the efficacy and additional safety parameters of GDHT guided by non-invasive advanced hemodynamic monitoring versus hemodynamic management guided by standard vital signs monitoring.

Secondary endpoints are as follows:

1.) Additional safety information

Monitored parameters:

- Duration of surgery (min)
- LOS (day of admission – day of discharge will be counted as 1 day)
- ICU LOS (day of admission – day of discharge will be counted as 1 day)
- 28-day mortality (number of patients who are not alive 28 days after randomization)
- Descriptive analysis of the incidence of any adverse events and reactions

2.) Comparison of hemodynamic characteristics and their changes over time between study groups

Monitored parameters:

- MAP (mmHg; before, after surgery)
- HR (Bpm; before, after surgery)
- SVV (%; before, after surgery)
- Number of episodes of hypotension¹
- Number of vasopressor administrations

3.) Comparison of laboratory values of selected blood parameters and their changes over time between study groups

Monitored parameters:

- Hemoglobin (g/l; before, after surgery and 24 hours after surgery)
- Plasma lactate level (mmol/L; before, after surgery and 24 hours after surgery)

4.) Comparison of fluid balance and fluid therapy between study groups

Monitored parameters:

- Volume of blood loss (ml/kg; during surgery² and in the 24-hour postoperative period)
- Urinary output (ml/kg/hod; during surgery² and in the 24-hour postoperative period)
- Number of administered units of packed RBC (during surgery² and in the 24-hour postoperative period)

¹ MAP bellow 65 torrs [18]

² **duration of surgery** is considered as the time from the skin incision to the suture of the dura

- Number of subjects receiving transfusion (during surgery² and in the 24-hour postoperative period)
- Crystalloid and colloid solutions consumption (type and total volume of infusion during surgery² and in the 24-hour postoperative period)
- Boluses of crystalloids (ml; during surgery²)

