8.6. Analysis sets

Full analysis set (FAS)

FAS comprises all randomized patients who underwent surgery. All endpoints will be evaluated using FAS.

Per-protocol set (PPS)

PPS includes all patients from FAS without protocol deviations which might affect the evaluation of primary endpoint. The principal investigator will assess protocol non-adherence on a case-by-case basis. Patients with significant deviations from the study protocol will be excluded from PPS.

PPS will be used for analysis of primary endpoint.

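### Minor: the planned tests on post-operative measurements do not adjust for the pre-operative value, and the interval shown beside Mann-Whitney does not match that test (exploratory secondary endpoints only)

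*Protocol*

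**What the plan says.** Protocol section 8 sets one rule for continuous variables: "For comparison between study arms two-sample Welch's t-test or its nonparametric alternative (Mann-Whitney test) will be used for continuous variables". Welch's test is used, with a difference in means, if normality is not rejected. If it is rejected, Mann-Whitney supplies the p-value and "Otherwise, the difference between the medians will be presented together with 95% CI calculated using bootstrap method". The type of bootstrap is not named. Descriptive tables give "mean, standard deviation, median, 25% and 75% quartile, minimum and maximum". There is no formal hypothesis, and "all statistical tests will be two-sided and performed on exploratory basis only", with p<0.05 called significant.

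Section 8.3 applies these tests to every secondary endpoint on the full analysis set (section 8.6: "FAS comprises all randomized patients who underwent surgery"). For hemodynamics, hemoglobin and lactate, the values and "their changes over time will be analysed descriptively and compared between study arms". No model with the pre-operative value as a covariate is named. "ICU and hospital length of stay (LOS) will be calculated as a number of days between admission and discharge", so they are whole days. Section 2.3 also lists counts, among them "Number of episodes of hypotension", vasopressor administrations and units of packed red cells. It records MAP, heart rate and SVV before and after surgery, and hemoglobin and lactate also at 24 hours.

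**The concern.** There are two separate issues, both confined to exploratory secondary endpoints.

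**Precision.** Each patient's MAP, heart rate, hemoglobin and lactate are measured before surgery. A comparison of post-operative values ignores that measurement. A comparison of changes subtracts it in full, which over-corrects when the correlation is below 1. Using it as a covariate takes the right amount. What is at stake is wider intervals and lower power than the same data would allow.

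**Mismatch of test and interval.** Mann-Whitney asks whether a patient in one arm tends to have a lower value than a patient in the other. The difference in medians is another quantity. With whole-day or count data the sample median moves in steps, so a bootstrap limit can fall on exactly 0 while the rank test is clearly significant. A report could then show an ICU stay difference of −2 to 0 days beside a p-value of about 0.004, and some readers would take the interval to mean no difference.

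**Working it through.** **Numbers per arm.** Section 8.1 gives 33% versus 11%, two-sided 0.05, 80% power and 10% dropout. Fisher's exact test has 81.4% power at 63 per arm, and 63/0.9 = 70, so the stated total of 140 is reproduced. The checks below use 70 per arm.

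**Precision.** Assume equal variance σ² before and after surgery and in both arms, and correlation r. With n per arm, the variance of the estimated difference between arms is:
- post-operative value: 2σ²/n
- change: 2σ²·2(1−r)/n
- ANCOVA: 2σ²(1−r²)/n

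The interval-width ratio of ANCOVA is therefore √((1+r)/2) against change and √(1−r²) against the post-operative value. The protocol gives no correlations, so a range is shown.

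| r | ANCOVA / change | ANCOVA / post-operative |
|---|---|---|
| 0.3 | √0.65 = 0.81 (19% narrower) | √0.91 = 0.95 (5%) |
| 0.5 | √0.75 = 0.87 (13%) | √0.75 = 0.87 (13%) |
| 0.7 | √0.85 = 0.92 (8%) | √0.51 = 0.71 (29%) |

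Simulation with 4000 trials at each of 63 and 70 per arm agrees (0.81, 0.87, 0.925 and 0.957, 0.869, 0.717). At r = 0.5 the variance ratio of 0.75 is worth 70/0.75 = 93 patients per arm under either planned comparison. At r = 0.1 ANCOVA has the same width as the post-operative comparison (ratio 1.00), so nothing is lost.

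Lactate is likely to be skewed. With an assumed log-scale SD of 0.45, a true 20% reduction and 70 per arm, log-scale ANCOVA has power 87%, 93% and 98% at r = 0.3, 0.5 and 0.7. Mann-Whitney on changes has 72%, 85% and 96%, and on post-operative values 82%. The type I error of the log-scale ANCOVA was 4.5–5.0%.

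**Mismatch.** Lengths of stay were simulated as lognormal values rounded up to whole days (log-SD 0.6), and counts as negative binomial with size 1. One scenario uses a figure from the protocol. Section 1.2.2 reports ICU stays of 3 [1–5] and 6 [3–11] days in an earlier brain-surgery trial. Read as medians and quartiles, these give log-SDs of ln(5/1)/1.349 = 1.19 and ln(11/3)/1.349 = 0.96; values of 1.1 and 1.0 were used. Normality was rejected in at least one arm of every simulated trial, so the Mann-Whitney branch applies.

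Share of all simulated trials with p<0.05 and an interval with a limit at exactly 0 / strictly straddling 0, at 70 per arm (ranges cover repeated simulation):

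| Scenario | Percentile bootstrap | Basic bootstrap |
|---|---|---|
| ICU stay, medians 3 vs 6 d | 11–12% / 1.4–1.6% | 16% / 14% |
| ICU stay, means 2.9 vs 3.7 d | 68–73% / about 1% | 49% / 7% |
| Hospital stay, means 8.9 vs 11.3 d | 22–25% / 11–14% | 15–16% / 19–22% |
| Hypotension episodes, 1 vs 2 | 71% / 1.8% | 50% / 10% |
| Vasopressor administrations, 2 vs 4 | 46% / 6% | 26% / 20% |

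Adding the two percentile figures gives about 12–13% for 3 versus 6 days and about 33–75% for the other rows. With the wide spread of section 1.2.2, ICU medians of 4 vs 6 d give 29% + 9% = 38%, and 4.5 vs 6 d give 20% + 9% = 29%. The lowest figure, 24%, came from hospital medians of 8 vs 7 d (log-SD 0.5), where only 33% of trials reach p<0.05 and 72% of those have an interval including 0. For red-cell units with 8% versus 25% transfused, the interval is [0, 0] in 77% of trials.

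Whole-day rounding is only part of the cause. With unrounded lognormal stays (medians 8 vs 6.5 d) no limit falls on exactly 0, yet 30–32% of trials with p<0.05 still have an interval that includes 0. The median difference is simply less sensitive than the rank test. With no true difference, Mann-Whitney rejects in 3.9–5.5% of trials.

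**Which interval agrees with the test.** Among trials with p<0.05, a Hodges-Lehmann interval still includes 0 in 52–100%, because ties remain. A bootstrap interval for the mean difference includes 0 in 2–18%. A large-sample interval for the Mann-Whitney probability never included one half, and the Brunner-Munzel form disagreed with the p-value in at most 0.8%.

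**The case against.** The strongest case against has four parts.

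- **The pre-operative values are used.** This is correct. A reader might infer that they are ignored, but section 8.3 compares changes over time, and a change score is more precise than the post-operative value once r exceeds 0.5. What stands is that both planned comparisons are less precise than ANCOVA at each correlation shown.
- **A separate SAP may add covariate adjustment.** It may. But section 8 already names the two-sample tests and section 8.3 assigns them to these endpoints, so the point concerns a stated choice and not an omission. This objection does keep the grade low.
- **The mismatch rates rest on assumptions.** They do. Only the 3 versus 6 day scenario is tied to a figure in the protocol, and it gives 12–13%. Section 8 speaks of continuous variables, so applying its rule to counts is an inference, although no other method is given for them. A reader might also infer that the interval merely touches 0 and seldom straddles it. That fails under the basic bootstrap, which the wording permits: for hospital stay, straddling is then the more common of the two.
- **No wrong conclusion follows.** Significance is read from the p-value, means and quartiles are also printed, and section 2.3 lists the number of patients transfused beside the units. This largely stands. The defect is that the only interval shown is a poor companion to its test.

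**Conclusion.** The point holds as a minor one, on exploratory secondary endpoints.

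The main part is precision. The planned comparisons are unbiased but give wider intervals than the data allow. ANCOVA narrows them by about 8–19% against changes and 5–29% against post-operative values for correlations from 0.3 to 0.7. The correlations are assumed; the formulas are standard and do not depend on the trial's results.

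The second part is reporting. The bootstrap interval for the median difference answers a different question from Mann-Whitney and can touch or include 0 beside p<0.05. The mechanism is certain. Its frequency is not, because it depends on the distributions, the effect and the unnamed bootstrap type. Under the percentile bootstrap at 70 per arm it is 12–13% in the scenario tied to the protocol, and mostly 35–75% for smaller assumed effects.

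A reader might go further and infer false positives, or a fault in the primary analysis or the sample size. Nothing supports that. Type I error is not inflated, and the primary comparison of proportions and the total of 140 are untouched.

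**What to change.** 1. **MAP, heart rate, hemoglobin, lactate.** Analyse each post-operative value, and the 24-hour value for hemoglobin and lactate, by ANCOVA on arm and pre-operative value, with the adjusted difference and 95% CI. Pre-specify lactate on the log scale, reported as a ratio, so that the scale is not chosen after looking at residuals. Include SVV only if a pre-operative SVV is recorded in both arms; section 6.3 describes the Starling monitor for the GDHT arm only.
2. **ICU and hospital stay, and the counts if the section 8 rule is applied to them.** Keep medians, quartiles and the median or mean difference as descriptive sizes in days, episodes or units. Beside the Mann-Whitney p-value, add the probability that a GDHT patient has the lower value (ties counted half) with its Brunner-Munzel 95% CI. A Hodges-Lehmann interval would not solve the problem.

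The cost is wording in section 8 or the SAP, which is to be finalized before database lock, and standard code. No new data, visits or patients are needed. The one small downside is that the probability measure is less familiar to readers, which is why the sizes in natural units stay beside it.
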